All statistical analyses will be performed at the QEII Health Sciences Center using SAS version 9.2 (Cary, North Carolina). Data validation will be an integral part of this protocol and will be carried out using already established clinical and administrative patient databases available through the Division of Cardiac Surgery at the QEIIHSC. This will ensure 100% follow-up of all patients and data accuracy. ~~All discrepancy will be investigated by the clinical outcomes committee.~~ **The Data and Safety Monitoring Committee will investigate all discrepancies.** The Maritime Heart Center (MHC) cardiac surgery database is a prospectively collected, clinical database that captures detailed information on a wide range of pre-operative, intra-operative, and in-hospital post-operative variables including post-operative complications and in-hospital mortality for all patients undergoing cardiac surgery at the QE II Health Sciences Center. It is audited on an annual basis to ensure reliability of data capture. The MHC cardiac surgery database will be linked to the Canadian Institute for Health Information (CIHI) Discharge Abstract Database and the Nova Scotia Vital Statistics database through the Population Health Research Unit (PHRU) at Dalhousie University. The CIHI Discharge Abstract Database is a national administrative database that contains extensive data on all admissions to hospital and enables us to track all

Capital Health

readmissions to hospital. The Nova Scotia Vital Statistics database collects information on all deaths occurring within the province of Nova Scotia and enables us to track all-cause mortality following discharge from hospital. The following data will be obtained from the MHC-PHRU data link after 6-months follow-up for all patients:

- i) Cardiac related mortality
- ii) Readmission to hospital for acute myocardial infarction (AMI), acute coronary syndrome (ACS), or congestive heart failure (CHF)
- iii) Re-intervention including CABG and/or PCI

Estimated Recruitment Rate

Approximately 200 complex cardiac procedures are performed annually in Halifax by nine cardiac surgeons. Of these patients, conflicting studies and patients being disqualified on the basis of exclusion criteria will result in a maximal annual number of eligible patients of 100 per year. We would plan to recruit 222 patients for this study. With a length of follow up of 6 months and using administrative data of an already well established data base we are expecting a rate of loss under 5%.

DATA HANDLING AND RECORD KEEPING

Data will be collected from patient charts and health records, the anesthetic record as well as the Maritime heart center cardiac surgery database. A data collection sheet will be filled out by the study nurse for patients included in the study. Follow-up data will be collected from patients themselves. In cases where patients have adverse outcomes, this information will be obtained from hospital records and the patient.

A data collection form will be used to collect study information and will be completed by the designated study personnel for participants. These forms will be detailing demographic characteristics, intra-operative, postoperative and follow-up outcomes. Individual data forms will record: the perioperative amount of blood products used (packed red cells, FFP, platelets,

Capital Health

Cryo). Also fibrinogen levels, hematocrit, PTT, INR, platelet count, Hemoglobin, Thromboelastometry (ROTEM®, CT, CFT, Angle, MCF), CVICU-stay, Hospital-stay, In-Hospital Mortality, Hemoglobin, adverse events (anaphylaxis, stroke, myocardial infarction, pulmonary embolism, and deep vein thromboembolism) and usage of factor VII concentrate and human prothrombin complex will be collected for study purposes. All data will be reviewed by the appropriate **outcome** committee. Once reviewed all data will be entered and maintained electronically on a designated CDHA computer.

Data will also be collected using the Maritime Heart Center (MHC) cardiac surgery database. This database is a prospectively collected, clinical database that captures detailed information on a wide range of pre-operative, intra-operative, and in-hospital postoperative variables including post-operative complications and in-hospital mortality for all patients undergoing cardiac surgery at the QE II Health Sciences Center.

QUALITY CONTROL AND QUALITY ASSURANCE PROCEDURES

Data validation will be an integral part of this protocol and will be carried out using already established clinical and administrative patient databases available through the Division of Cardiac Surgery at the QEIIHSC. This will ensure 100% follow-up of all patients and data accuracy. **The Data and Safety Monitoring Committee will investigate all discrepancies.**

Monitoring

The study will be monitored in accordance with ICH-GCP guidelines that require a minimum of three visits, before the trial starts, once during the trial, and after the trial is completed.

Data Storage

[figure not shown]

Capital Health

During the study data will be stored in a filing cabinet in a designated office for the study nurse as well as a CDHA computer, as a data file. All other data will be stored on the CDHA network. Once the study is complete, data will be stored in a filing cabinet in the Principal investigator's office under lock and key. All other data will be stored as per current standard of practice for elective cardiac surgery patients; on the CDHA network and in the Maritime Heart Center (MHC) cardiac surgery database. De-identified information will be available to the sponsor after study completion. In case of adverse outcomes, the study will be unblinded and may be reviewed by regulatory agencies through CDHA. The research team also intends to publish de-identified in a research journal that will be available to the study participants and to the public.

~~Prior to data transfer to CSL Behring, study participant information will be de-identified using a serial number system. This unique number will be assigned to each study participant and will be stored on paper in a filing cabinet in a designated, secure office in the Department of Anesthesia.~~ The study research data will be archived for a minimum of 25 years according to the current Capital Health policy. Once the information requires destruction, paper data will be shredded through the hospital confidential waste disposal. Electronic data will be deleted from the designated CDHA computer. Data stored independently on the CDHA hospital network and the Maritime Heart Center database will be disposed of by the regulations governing those networks or databases.

Figure 1. ROTEM® Parameters

CT (clotting time): time from start of measurement until initiation of clotting
 => initiation of clotting, thrombin formation, start of clot polymerisation

CFT (clot formation time): time from initiation of clotting until a clot firmness of 20mm is detected
 => fibrin polymerisation, stabilisation of the clot with thrombocytes and F XIII

MCF (maximum clot firmness): firmness of the clot
 => increasing stabilisation of the clot by the polymerised fibrin, thrombocytes as well as F XIII

ML (maximum lysis): reduction of the clot firmness after MCF in relation to MCF
 => stability of the clot (ML < 15%) or fibrinolysis (ML > 15% within 1h)

Figure 2. FIBTEM® Test Specificities

[figure not shown]
[figure not shown]
FIBTEM:

- activation as in **EXTEM**
- platelet inhibition reagent added

TEMogram shows isolated fibrinogen contribution to Clot firmness

- A)
- **EXTEM:** amplitude low
 - **FIBTEM:** amplitude normal
- => fibrinogen level OK
=> platelet deficiency

- B)
- **EXTEM:** amplitude low
 - **FIBTEM:** amplitude low
- => fibrinogen deficiency

[figure not shown]
[figure not shown]

Figure 3. Treatment Algorithm

[figure not shown]

Table 1. Sample Size Calculation

	Relative Risk Reduction in Mean Number of Units Transfused			
Power = 1-beta	30% $\Delta = 1.0$ units (3.4 to 2.4)	50% $\Delta = 1.7$ units (3.4 to 1.7)	70% $\Delta = 2.4$ units (3.4 to 1.0)	90% $\Delta = 3.1$ units (3.4 to 0.3)
80%	634	220	111	69
90%	848	295	149	92
95%	1049	364	183	113

Table 2. Schedule of Assessments

	Preop I+II	Intraop I	Intraop II	Intraop III	Postop I	Postop II	Postop III	Postop IV
Time intervals	Baseline	On Bypass Aortic Clamp Off	Off Bypass After Heparin reversal (5-15 minutes post protamine)	10 minutes after administration (+5 minutes)	End of Surgery (+10 minutes)	Blood Draw 12 Hours (+60 minutes)	Blood Draw 24 Hours (+60 minutes)	Discharge
Primary Outcome					Total Blood Components Used	Total Blood Components Used	Total Blood Components Used	Total Blood Components Used
					Cryo Used	Cryo Used	Cryo Used	Cryo Used
					FFP Used	FFP Used	FFP Used	FFP Used
					Packed Red Cells Used	Packed Red Cells Used	Packed Red Cells Used	Packed Red Cells Used
					Platelets Used	Platelets Used	Platelets Used	Platelets Used
Secondary Outcomes	Fibrinogen Levels		Fibrinogen Levels	Fibrinogen Levels	Fibrinogen Levels	Fibrinogen Levels	Fibrinogen Levels	Adverse Effects
	Hematocrit		Hematocrit	Hematocrit	Hematocrit	Hematocrit	Hematocrit	Anaphylaxis
	Hemoglobin	ABG/ Hemoglobin	ABG/ Hemoglobin	ABG/ Hemoglobin	ABG/ Hemoglobin	Hemoglobin	Hemoglobin	CVICU LOS
	INR/PT		INR/PT	INR/PT	INR/PT	INR/PT	INR/PT	Deep Vein Thromboembolism
	Platelet Count		Platelet Count	Platelet Count	Platelet Count	Platelet Count	Platelet Count	Hospital LOS
	PTT		PTT	PTT	PTT	PTT	PTT	
	*ACT	ACT	ACT	ACT	ACT		Blood Drainage	In Hospital Mortality
	*EXTEM	EXTEM	EXTEM	EXTEM	EXTEM	EXTEM	EXTEM	Myocardial Infarction
	*INTEM		INTEM	INTEM	INTEM	INTEM	INTEM	Pulmonary Embolism
	*FIBTEM	FIBTEM	FIBTEM	FIBTEM	FIBTEM	FIBTEM	FIBTEM	Stroke
			HEPTEM	HEPTEM	HEPTEM	HEPTEM	HEPTEM	
	AT III		Usage of Factor VII a	Usage of Factor VII a	Usage of Factor VII a	Usage of Factor VII a	Usage of Factor VII a	Usage of Factor VII a
	*ABG		Usage of human prothrombin complex	Usage of human prothrombin complex	Usage of human prothrombin complex	Usage of human prothrombin complex	Usage of human prothrombin complex	Usage of human prothrombin complex

Please Note: 24 hour blood draw = primary endpoint highlighted in green, assessments highlighted in peach are outside

*the standard of care ,
Preoperative 1- assessments done in Same day admission or on the floor the day prior to OR
Only these values will be done on the Preoperative II time point. Preoperative II (window is +10 minutes post art line insertion)

Table 2. Schedule of Assessments (continued)

Time intervals	6 week post operative clinic visit (+1week) (phone visit may occur if patient is not brought in within window)	3 month phone visit (+1week)	6 month phone visit (+1week)
Secondary Outcomes	
 • Angina • Re-admission (CHF, AMI, ACS) • Incisional wound infection • Thrombosis • MI • Angiography • PCI (percutaneous coronary intervention) • Repeat cardiac surgery • Cardiac Mortality 	
 • Angina • Re-admission (CHF, AMI, ACS) • Incisional wound infection • Thrombosis • MI • Angiography • PCI (percutaneous coronary intervention) • Repeat cardiac surgery • Cardiac Mortality 	
 • Angina • Re-admission (CHF, AMI, ACS) • Incisional wound infection • Thrombosis • MI • Angiography • PCI (percutaneous coronary intervention) • Repeat cardiac surgery • Cardiac Mortality

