Hypothesis: The aim of the study is to show that **prophylactic** first line treatment with concentrated fibrinogen prior to conventional therapy with FFP, platelets, Cryo, and other blood products such as factor VII concentrate and human prothrombin complex (factors II, VII, IX, X) has superiority over conventional therapy alone (**"wait and see"**) in **perioperative management of bleeding** patients with **low or low normal fibrinogen levels ($\leq 3.8\text{g/l}$)** after complex cardiac surgery.

Primary objective: To determine the cumulative perioperative amount (number of units) of blood components used between the start of surgery and 24 hours after administration of the study drug or placebo. 'Blood Components' are defined as all fresh components of blood (PRBCs, plasma, platelets, and Cryo).

Secondary objective: To determine the effect of RiaSTAP™ on fibrinogen levels, hematocrit, prothrombin time (PT), partial thromboplastin time (PTT), international normalized ratio (INR), platelet count, hemoglobin, thromboelastometry* (ROTEM®, EXTEM, INTEM, HEPTM, FIBTEM test, Clotting Time, Clot Formation Time, Angle, Maximum Clot Firmness), CVICU-stay, Hospital-stay, In-Hospital Mortality, adverse events (anaphylaxis, stroke, myocardial infarction, pulmonary embolism, and deep vein thromboembolism) and usage of factor VII concentrate and human prothrombin complex (factors II, VII, IX, X), total avoidance of transfusion after CPB (24h after administration of study drug or placebo).

*Thromboelastometry (ROTEM®; Pentapharm GmbH, Munich, Germany) is a bedside qualitative test of whole blood coagulation (Figure 1). The Clotting Time (CT) represents the time required for initial fibrin formation. Both Clot Formation Time (CFT) and angle represent the rate of clot formation, fibrin cross-linking, and platelet-fibrin interaction. Maximum Clot Firmness (MCF) represents the overall clot quality determined by

Capital Health

polymerised fibrin, platelets and factor XIII. The ROTEM[®] system provides several tests, one of them is the FIBTEM[®] test. The FIBTEM[®] test shows the isolated fibrinogen contribution to the clot firmness (Figure 2).

TRIAL DESIGN

Primary and secondary outcomes

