Tranexamic acid (Sandoz Canada Inc.) will be infused at a rate of 2mg/kg/hr following an initial bolus of 1000-2000mg. During the cardiopulmonary bypass run, propofol will be infused with subsequent boluses of fentanyl or sufentanil. Prior to cardiopulmonary bypass, patients will be given unfractionated heparin (500 units/kg; PPC, Pharmaceuticals Partners of Canada Inc.) to maintain an activated clotting time (ACT) > 480 seconds. The cardiopulmonary bypass circuit includes a membrane oxygenator and roller pumps to maintain a non-pulsatile perfusion technique. Depending on the procedure, deep or moderate hypothermia (nasopharyngeal temperature of 18 or 32 to 34°C) will be utilized and cardioprotection will be maintained using antegrade and retrograde cold blood cardioplegia when possible. Separation from cardiopulmonary bypass will be achieved once the patient is re-warmed to a nasopharyngeal temperature of 36.5°C. Following separation from cardiopulmonary bypass, heparin will be reversed with protamine (1mg protamine/100units heparin; protamine sulphate, Sandoz Canada Inc.). A hemoglobin concentration below 70 g/l will be treated with PRBCs to maintain a hemoglobin of 70 g/l or greater throughout the procedure.

Capital Health

Surgical technique

As per standard of care in this surgical population and depending on the procedure, a median sternotomy or lateral thoracotomy will be performed in all patients. Surgery will be performed in a standardized fashion with CPB. During CPB, the mean arterial pressure target will be 60-70 mmHg and the body temperature will be allowed to drift to approximately 32°C or lower. Intermittent cold blood cardioplegia (1:4 blood to crystalloid with maximal K⁺ concentration 22 meq/L) will be delivered antegrade via the aortic root unless otherwise indicated. No special blood conservation technique will be utilized other than: non-hemic prime, retransfusion of all contents of the oxygenator at the end of CPB, and acceptance of normovolemic anemia. Post-operatively non-hemic volume expanders are utilized routinely (Voluven®, Kabi Fresenius Inc., Germany).

Post-operative management

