As per the standard of care in this surgical population, all post-operative cardiac surgery patients will be taken immediately to a dedicated cardiovascular intensive care unit (CVICU). All patients will receive respiratory and hemodynamic support as needed. Each patient will be required to meet standard hospital criteria both prior to extubation and prior to transfer to the intermediate-care unit (IMCU). Discharged patients will be transferred to an intermediate-care unit or general-care ward under the care of the same cardiac surgical team. All patients will be monitored continuously for a minimum of 24 hours. In case of a post-operative bleeding in CVICU the same algorithm (Figure 3) like in the OR will be used. In case of surgical bleeding a re-sternotomy will be performed. Diffuse bleeding will be treated with blood components (step 2 -5, Figure 3). Patients having a valve replaced with a mechanical valve will receive heparin or warfarin 48 hours after surgery. All other patients will get ASA (acetylsalicylic acid, Aspirin®, Bayer Canada) on the first postoperative day (anticoagulation protocol, Division of Cardiac Surgery, QEII, Halifax, Canada).

ASSESSMENT OF SAFETY

Adverse Events

The following treatment-emergent and adverse effects will be captured during this study from the date ~~the consent was signed~~ of randomization to the 6 month follow-up:

Treatment-emergent adverse events

- Pleural effusion
- Atrial fibrillation
- Postoperative Delirium
- Reoperation because of surgical bleeding and unknown bleeding
- Air embolism

Adverse events (A/E) and Serious adverse events (SAE)

- Anaphylaxis
- Stroke
- Myocardial infarction
- Pulmonary embolism
- Deep vein thromboembolism
- Sternal wound infection
- Recurrent angina
- Angiography
- Percutaneous coronary intervention (PCT)
- Repeated cardiac surgery
- Cardiorespiratory arrest
- Cerebral hemorrhage
- Death

All serious unexpected adverse drug reactions will be reported to Health Canada as per ICH/GCP guidelines.

Unblinding

Unblinding for this study will occur when:

1. Clinical treatment decisions need to be made and when an unexpected serious adverse event occurs and the intervention must be made known.
2. At the request of the Data Safety Monitoring Committee.

Capital Health

3. After 110 participants have reached the primary endpoint for interim analysis.
4. At the conclusion of the study to determine the effect of the intervention.

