The Blood Transfusion Services are able to unblind for the clinical treatment of a patient. Please refer to the site Standard operating procedure for more details of this process. If a patient's treatment is unblinded before the 24 hour primary end point their data will not be used in the analysis.

STATISTICS

Sample size

The primary outcome of interest will be overall need for blood transfusion at 24hr after surgery (including all used blood components from the start of surgery). For the sample size calculations G*Power version 3.1.2 was used.

Based on the available literature ^{9,10,12}, the investigator hypothesized a 70-90% reduction in total units of blood products in the group receiving fibrinogen compared with the group receiving conventional therapy. An estimate of blood product requirement in the group receiving conventional therapy is mean 3.4 units (standard deviation 5.9) based on our data from 2005 to 2007 for AVR+CABG, MVR+CABG, AVR+MVR, and Aortic root repair +/-AVR. Standard deviation 5.9 was used for both groups. Blood product requirement in the two groups will be compared using the Mann-Whitney U test for two independent samples. The sample size calculation was based on a two-tailed test with $\alpha = 0.05$, for $\beta = 0.2, 0.1, \text{ and } 0.05$. The sample sizes shown Table 1 represent the number of patients required in each group.

Details of the planned analysis

~~Individual case forms will be completed by the research coordinator for individual patients.~~ **The research coordinator will complete individual case forms for individual patients.** These forms will be detailing demographic characteristics,

Capital Health

intra-operative, post-operative and follow-up outcomes. Outcome data and blood samples will be collected according a lab/data schedule (Table 2). ~~All data will be reviewed by the appropriate clinical outcomes committee.~~ **The Sponsor will review all data.** Once reviewed all data will entered and maintained electronically.

Primary outcome: Blood component requirement in the two groups will be compared using the Mann-Whitney U test for two independent samples.

Secondary outcomes: Univariate comparisons between patients randomized to FIB and patients randomized to PLACEBO group will be carried out based on pre-, intra-, and post-operative variables using Chi-square tests for dichotomous variables, two-tailed t-tests for continuous variables and Wilcoxon rank sum tests for nominal variables.

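### No time point is named for the effect of RiaSTAP on fibrinogen, coagulation and ROTEM values, and three of the four post-dose samples follow possible component therapy

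*Combined protocol and SAP*

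**What the plan says.** The Secondary objective (Trial Objectives and Purpose) is the effect of RiaSTAP "on fibrinogen levels, hematocrit, prothrombin time (PT), partial thromboplastin time (PTT), international normalized ratio (INR), platelet count, hemoglobin", followed by the ROTEM tests and clinical outcomes. Neither this list nor the list of secondary outcomes under Trial Design gives a time for the laboratory values.

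Table 2 schedules these values once after heparin reversal (Intraop II) and at four times after study drug:
- Intraop III: "10 minutes after administration (+5 minutes"
- Postop I: "End of Surgery (+10 minutes"
- Postop II: "Blood Draw 12 Hours (+60 minutes"
- Postop III: "Blood Draw 24 Hours (+60 minutes"

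The In-Hospital Follow-up paragraphs, under Methodology and under Planned Frequency and Duration of Follow-up, list blood work only at end of surgery, 12 h and 24 h. The 10-minute sample appears only in Table 2.

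Components can be given between study drug and the later samples. Post-operative management says: "Diffuse bleeding will be treated with blood components (step 2 -5, Figure 3". Anaesthesia management adds: "A hemoglobin concentration below 70 g/l will be treated with PRBCs to maintain a hemoglobin of 70 g/l or greater throughout the procedure".

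For continuous secondary outcomes, Details of the planned analysis names "two-tailed t-tests for continuous variables". It gives no time point, no baseline adjustment and no handling of components received before a sample.

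**The concern.** Each component acts on a listed outcome: Cryo and plasma on fibrinogen, FIBTEM and the clotting times, platelets on platelet count and EXTEM, red cells on hemoglobin and hematocrit. The plan recognises this for fibrinogen. Subject withdrawal criteria orders a FIBTEM before the Cryo step so that concentrate and Cryo do not add up to an excessive level.

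If the primary hypothesis is right, placebo patients receive more components than fibrinogen patients. A late sample then compares concentrate plus few components with saline plus more. Similar 24 h fibrinogen or INR could be reported as little or no effect of RiaSTAP when part of the placebo value came from transfusion. Someone who follows the text rather than Table 2 would use only the three samples open to this, and could choose among them after seeing the data.

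**Working it through.** **1. Position of the samples.** Four post-dose samples are scheduled. Three (end of surgery, 12 h, 24 h) come after the component steps may have acted. The text names those three and omits the fourth.

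**2. Expected imbalance.** Sample size gives a control mean of 3.4 units (SD 5.9) and a hypothesized reduction of 70-90%. Table 1 turns this into differences of 2.4 units (3.4 to 1.0) and 3.1 units (3.4 to 0.3).

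**3. The plan's dose formula.** Dosage and Dosage Regimen: dose (g) = mm × kg / 140. The worked example, 12 mm at 75 kg, gives 12 × 75 / 140 = 6.43 g; the plan states 6.4 g. Inverted, rise (mm) = g × 140 / 75 at 75 kg.

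**4. Upper-end shift from Cryo.** Background Information gives 150-450 mg fibrinogen per Cryo unit, guaranteed in 75% of units. Assume that every unit is Cryo, that its fibrinogen acts gram for gram like concentrate, and that nothing is lost before the sample.

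| Units taken as Cryo | Fibrinogen (g) | FIBTEM (mm, 75 kg) | Share of 12 mm |
|---|---|---|---|
| 3.4 (control mean) | 0.51-1.53 | 0.95-2.86 | 8-24% |
| 2.4 (difference at 70%) | 0.36-1.08 | 0.67-2.02 | 6-17% |

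The first row is the extreme in which the fibrinogen arm receives none. The true mix also includes red cells, plasma and platelets, so both rows lie at the upper end for these unit counts.

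**5. A second route, in g/L.** The section on clinical impact gives transfusion rates of 38% (all cardiac cases) and 60% (AVR+CABG). Assume that the 70-90% reduction applies to the share transfused, and that transfused patients gain 0.25-1.0 g/L on average. The upper value is the median rise quoted in Background Information for 30 ml/kg of plasma; the lower is assumed. Narrowing of the between-arm difference = share × reduction × rise:
- low: 0.38 × 0.70 × 0.25 = 0.07 g/L
- high: 0.60 × 0.90 × 1.0 = 0.54 g/L
- equal transfusion in both arms: 0

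**6. Choice left open.** Seven named laboratory values at four samples make 28 possible tests. At 0.05 with no effect anywhere, 28 × 0.05 = 1.4 false positives are expected. The plan does not say which of the 28 answers the objective.

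**The case against.** The strongest reply is that late values remain randomized. The Hypothesis compares first-line fibrinogen ahead of conventional therapy with conventional therapy alone, which is a comparison of strategies, and 12 h or 24 h values estimate the effect of assignment under it. This stands. A reader might infer that the later samples say nothing valid about RiaSTAP; the documents do not support that. Those samples do not isolate the drug's own effect, and the plan does not say which effect it means.

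A reader might also infer that the algorithm will have corrected these values, and more so under placebo, as a fact. The readable text ties later steps to ongoing bleeding. Its only laboratory trigger for transfusion is hemoglobin below 70 g/l, in both arms. At the 60% rate about 40% of comparable patients receive nothing. The excess under placebo is the trial's hypothesis, and the 3.4 units count from the start of surgery, so some precede study drug. Figure 3 is not shown, so other triggers cannot be checked.

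A larger loss is easy to construct: ten Cryo units in one 75 kg placebo patient give 1.5-4.5 g, or 2.8-8.4 mm, which is 23-70% of 12 mm. But ten units is an assumption about one patient and says nothing about arm means.

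The 10-minute sample has limits too. Hemoglobin and hematocrit may then mainly reflect infused volume (6.4 g at 20 g/L is 320 ml), and any benefit through less bleeding needs time. Red cells may also already have been given. So that sample suits fibrinogen and ROTEM, and later hemoglobin, hematocrit, platelets and INR should still be analysed.

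**Conclusion.** The concern holds in a limited form. The objective is worded as a drug effect, the text points to three samples that components may already have changed, and the analysis is an unadjusted t-test at no stated time, although better-placed samples are already scheduled. The direct effect on fibrinogen and FIBTEM may be attenuated.

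The size is uncertain. It is about 8-24% of the 12 mm example if the whole control mean were Cryo, and zero if the arms are transfused equally. The figure rests on the assumptions in step 4 of the working and on 3.4 units applying to the patients randomized. That mean comes from 2005-2007 surgical data. Subject withdrawal criteria says patients without diffuse bleeding are not randomized; if so, the trial mean could be higher.

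The primary outcome and the sample size are unaffected.

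**What to change.** 1. In Details of the planned analysis, name Intraop III (10 minutes after administration), adjusted for Intraop II, as the analysis of the direct effect on fibrinogen and FIBTEM/ROTEM. A regression of the Intraop III value on arm and the Intraop II value would do this. State that the Intraop II draw precedes study drug.
2. Add the 10-minute sample to both In-Hospital Follow-up paragraphs so that they agree with Table 2.
3. Report end-of-surgery, 12 h and 24 h values, including hemoglobin, hematocrit, platelets and INR, as randomized comparisons of the two treatment strategies. Show them beside the components each arm had received by that time, and do not read them as the drug's isolated effect. Table 2 already records components at these three times. Components given before the 10-minute draw should be tabulated as well.

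The cost is wording, with no new samples and no change in N. The downside is that the later time points become supportive for the direct-effect question. They lose no confirmatory standing, since the plan gives them none.
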